3.1 Problem of hyperkalemia

Patients with end stage renal disease (ESRD) who are treated with conventional hemodialysis (HD) schedules often exhibit life-threatening, episodic hyperkalemia. Reduced kidney function increases extracellular potassium concentration due to the combined effects of a net positive potassium balance in concert with disturbed ion distribution in the body fluid compartments ¹⁻². In the HD population, scheduled measurement of serum potassium concentration is typically performed only once or twice a month. Even with this restricted testing schedule, serum potassium exceeds 5 mEq/L in more than a third of patients ^{3,4}. However, episodes of hyperkalemia are likely much more common during conventional HD, since many of these transient events are not captured with standard treatment and testing schedules. Episodic hyperkalemia disrupts the electrophysiology of heart muscle and can promote cardiac arrhythmias. It is plausible that episodes of hyperkalemia contribute to the alarmingly high rate of sudden cardiac arrest, by far the most common cause of death in the HD population ^{5,6}. But consistent control of serum potassium levels is difficult in HD patients. Our own data suggest that 40-50% of HD patients who exhibit serum potassium concentrations > 5.5 mEq/L during routine measurements in one month will fail to be “cured” the following month with usual clinical care (unpublished data). One dilemma that arises is that reducing serum potassium with the use of low dialysate potassium is actually associated with an increased risk of sudden cardiac death ⁵. Furthermore, HD patients already carry a high pill burden, and it is unclear if prescription of an additional oral medication will reduce the frequency of episodic hyperkalemia ⁷. Even though the manner of achieving this ideal is unclear, these observations suggest that avoiding extremes in the concentrations of serum potassium will improve the cardiovascular risk in HD patients.

High serum potassium contributes to cardiac risk. Maintaining serum potassium homeostasis is critical to create a stable transmembrane potential of about -85 mV, and this permits normal cardiac and skeletal muscle function ⁸. Abrupt changes in serum potassium levels result in deviations in membrane potential that can lead to muscle paralysis and to fatal arrhythmias ⁸. In patients with ESRD, the ability to maintain potassium balance by the kidney is diminished, and therefore acceptable potassium conditions can only be approximated by dietary potassium restriction and clearance with dialysis. In a patient maintained on a conventional, three-times-per-week HD regimen, potassium intake is recommended to be limited to about 60 mEq/day (420 mEq/week). Dialysis removal typically is around 70-100 mEq per treatment (210-300 mEq/week for thrice-weekly schedules)². Assuming that native kidney function accomplishes minimal potassium clearance, to maintain a near-steady potassium concentration potassium elimination through the gastrointestinal tract is essential.

In the general population, the normal range for serum potassium is typically reported between 3.5 and 5.0 mEq/L but in HD patients the ideal serum potassium concentration tends to be higher. In a study of 2,134 HD patients, a pre-dialysis serum potassium level of 5.1 mEq/L was associated with the lowest risk of peri-dialytic sudden cardiac arrest, while potassium levels above and below 5.1 were associated with increasing risk ⁵. Another study examining pre-dialysis serum potassium levels and survival within a cohort of 81,013 hemodialysis patients, potassium concentrations between 4.6-5.3 mEq/L were associated with the lowest incidence of all-cause mortality ⁹ and a survey of 55,183 HD patients in the Dialysis Outcomes and Practice Patterns Study (DOPPS) multinational cohort confirmed that the lowest risk of death was observed among patients with serum potassium levels between 4 and 5.5 mEq/L and a significant increased risk of death and arrhythmia outcomes at potassium values ≥ 5.6 mEq/L ¹⁰. In a study of serum potassium values obtained within a large dialysis organization, approximately 20% of all serum potassium measurements were ≥ 5.5 mEq, and about 12.5% of measurements were ≥ 6.0 , whereas potassium < 4.0 accounted for only 9% of all measurements ⁴.

The removal of potassium from an individual receiving conventional HD departs dramatically from the physiology of a person who has normal kidney function. First of all, HD can only remove potassium from the extracellular fluid compartment, which contains just 2% of total body potassium ². Second, the rate of lowering of serum potassium concentration is inconstant, causing a rapid fall in serum potassium at the start of the HD treatment when the serum-to-dialysate gradient is highest. The abrupt drop in the first hour is followed by more gradual decline over next 2-3 hours, as the serum-to-dialysate potassium gradient narrows ¹¹. The final serum potassium concentration approaches that delivered in the dialysate. Third, the end of the HD session causes a subacute “rebound” of serum potassium levels as potassium mobilizes from the intracellular to the extracellular space. The magnitude and the time course of these potassium transients over the HD period are influenced by the initial serum potassium concentrations as well as by the other constituents of the dialysis prescription such as the amount of volume ultrafiltration, dialysate bicarbonate, glucose, and potassium concentrations ¹². The potential impact of excursions of potassium concentrations is compelling. In a study of ESRD patients on conventional treatment schedules who had wearable defibrillators in place, 70.0% of the captured arrhythmia events occurred during the HD session and 2.8% arrhythmias were observed immediately after the dialysis procedure ¹³.

It might seem as if the problem of hyperkalemia in ESRD can be managed by setting a very low dialysate potassium concentration. However, potential hazards may arise by reducing serum potassium levels too rapidly during HD treatments ¹⁴. Clearly a lack of consensus exists on the ideal dialysate potassium concentration to prescribe. Recent data from DOPPS reported the range of prevalent use of potassium dialysate <2 mEq/L from as low as 3% in the US to as high as 62% in Spain ¹⁰. The safety of low potassium dialysate has been a focus of concern given the possibility that dialysis-induced potassium reductions may provoke cardiac arrhythmias and sudden cardiac death. Multiple large retrospective studies investigated associations between dialysate potassium levels, serum potassium levels, and risk of sudden death, cardiac events, and all-cause mortality. In general, large cohort studies identified increased risks of sudden cardiac death associated with use of low potassium dialysate < 2 mEq/L ^{5,9}. The risks associated with low potassium dialysate are principally seen among patients with low to normal pre-dialysis serum potassium. No long-term, prospective, controlled studies have been conducted to examine the effect of low potassium dialysate on hard clinical outcomes, but several short term trials employed cardiac monitors to measure subclinical arrhythmic events such as ventricular ectopy, premature ventricular complexes, and changes in electrocardiographic conduction parameters ^{13,15}. Most but not all studies observed higher rates of ventricular ectopy and QTc interval prolongation associated with exposure to potassium dialysates of 0 or 1 mEq/L compared to higher potassium dialysate concentrations ^{14,16,17}. However, whether these observations also apply to clinical arrhythmic events or mortality is not known. In summary, circumstantial evidence highlights the hazards of using a low potassium dialysate <2 mEq/L, and the evidence for risk is strongest for patients with serum potassium levels <5 mEq/L. Whether lower potassium dialysate is appropriate or potentially beneficial for patients with higher serum potassium levels is unclear.

Alternatively, hyperkalemia in ESRD patients can potentially be managed with oral medications which can bind potassium. Sodium polystyrene sulfonate (SPS) has been available since the 1950s to treat high serum potassium levels, and it is approved for treatment of hyperkalemia by the US Food and Drug Administration (FDA) ¹⁸. However, SPS has not been rigorously studied. There is limited prospective, long-term clinical trial data available to understand the safety and efficacy of these agents, particularly in patients with ESRD. Patients experience adverse gastrointestinal symptoms with SPS, and its use has been associated with life-threatening colonic necrosis ¹⁹⁻²¹. In addition, a significant sodium load can occur with SPS, and this can be a particular concern in patients with ESRD ^{22,23}. These issues make the repeated or chronic administration of SPS not feasible, particularly in patients such as those with ESRD where the incidence of hyperkalemia is high. A safe and effective oral potassium binder has the potential to reduce the frequency of episodes of hyperkalemia and to limit large excursions in serum potassium values in ESRD patients treated with hemodialysis.

3.2 Clinical experience with patiromer

Relypsa recognized a need for a well-tolerated potassium binder to be used in both acute and chronic clinical settings. Relypsa developed an orally administered, non-absorbed, high-capacity serum potassium binder with physicochemical characteristics that might yield an effective product suitable for chronic use. Patiromer is composed of patiromer sorbitex calcium, a new chemical entity belonging to the pharmacologic class of Potassium Binders, and xanthan gum. The product consists of the polymer anion and a calcium-sorbitol counter-ion. The polymer anion is also termed “patiromer anion” or simply “patiromer,” and it is the active moiety. The resin is a cation-exchange polymer that binds potassium predominantly in the lumen of the colon where active potassium secretion occurs. This potassium binding leads to fecal potassium excretion, leading to removal of potassium from the body and lowering of serum potassium levels in the hyperkalemic patient. On October 21, 2015 the US FDA approved patiromer for use in patients with elevated potassium concentration in the body, based on data described below in section 3.4. The approved indication in the US for patiromer is the treatment of hyperkalemia.

3.3 Study rationale

Patients with ESRD who are treated with three times per week with HD are commonly exposed to the risk of high potassium in the blood (hyperkalemia). Serum potassium values above 5.5 mEq/L are associated with increased mortality. Hyperkalemia treatment options are limited in the ESRD population. The use of SPS is associated with poor patient tolerance and with serious adverse clinical risks; the prescription of low potassium dialysate (<2mEq/L) is associated with increased risk of cardiac arrest. Oral administration of patiromer is effective to decrease serum potassium in patients who have CKD and hyperkalemia, but it has not been studied extensively in HD patients. Either hyperkalemia or excursions in serum potassium concentrations may play a role in the high risk of sudden cardiac death in ESRD patients treated with HD. It is not known if once-daily dosing of patiromer will reduce the frequency of episodes of hyperkalemia in this vulnerable population.

It is important to review standard, usual care for ESRD patients who are treated with conventional HD schedules (thrice-weekly treatments), to avoid and treat episodes of hyperkalemia. If patients present at an emergency facility or hospital and are discovered to have hyperkalemia, they are typically treated with inhaled beta agonists, intravenous glucose and insulin, and/or intravenous calcium ²⁴. The latter does not treat the hyperkalemia *per se*, but it is intended to stabilize the myocardial cells and limit risk of depolarization. A single dose of SPS is often administered. If these medical interventions fail to resolve hyperkalemia, urgent hemodialysis is prescribed. In the outpatient setting, hyperkalemia may be detected at the start of the HD session. If there are no symptoms, patients receive hemodialysis with their usual prescriptions and no further interventions are prescribed. For all patients, the HD clinic-based dietitian will counsel on adherence with a low potassium diet, with the goal of limiting potassium intake to less than 60 mEq per day ^{25,26}. For this current protocol, the dietitian will be blinded to the assigned treatment for the course of the study. If pre-dialysis hyperkalemia is a recurrent problem, the physician and dialysis clinic team will review the prescribed dialysate. Due to the risk associated with prescription of low dialysate potassium, the outpatient clinics employed in this study do not prescribe dialysate potassium lower than 2 mEq/L. In rare instances, if hyperkalemia continues to recur despite these interventions, and additional HD treatments will be prescribed.

3.4 Dosing rationale

Three clinical studies primarily inform the recommended initial dose and titration of patiromer in those participants in this study who randomize to receive the drug. In the first study, 243 patients with chronic kidney disease (CKD) and hyperkalemia initially were treated with patiromer ²⁷. The starting dose was 8.4 or 16.8 g (as divided doses BID) for four weeks. With a mean daily dose of patiromer during the initial treatment phase of 12.8 g in patients with mild hyperkalemia and 21.4 g in patients with moderate-to-severe hyperkalemia, 76% of the participants reached the target range of serum potassium (3.8-5.1 mEq/L). Then the study had an 8-week period of randomized withdrawal from patiromer in 107 subjects. In the latter period, hyperkalemia occurred in 60% of the placebo-treated patients and only 15% of the patients who continued on patiromer ²⁷. In the second study, 304 subjects with hyperkalemia, CKD, type 2 diabetes, and hypertension were randomized to receive 1 of 3 randomized starting doses of patiromer (4.2 g [n = 74], 8.4 g [n = 74], or 12.6 g [n = 74] twice daily [mild hyperkalemia] or 8.4 g [n = 26], 12.6 g [n = 28], or 16.8 g [n = 30] twice daily [moderate hyperkalemia]) ²⁸. Patiromer was titrated to achieve and maintain serum potassium level 5.0 mEq/L or lower. At the end of the open label 52-week study the mean reduction from baseline in serum potassium level at week 4 in patients with mild hyperkalemia was 0.35 mEq/L for the 4.2 g twice daily starting-dose group, 0.51 mEq/L for the 8.4 g twice daily starting-dose group, and 0.55 mEq/L for the 12.6 g twice daily starting-dose group ²⁸. From week 4 through week 52, statistically significant mean decreases in serum potassium levels were observed at each monthly point in patients with mild and moderate hyperkalemia. The mean daily dose of patiromer after 4 weeks was 18.5 g for the patients with mild hyperkalemia and 26.9 g with moderate hyperkalemia.

The third relevant trial was the only study published to date that enrolled HD patients. In this study, six ESRD patients on HD were monitored for a 7-day baseline period, then they were administered patiromer 4.2g TID ²⁹. In this small study, the mean serum potassium decreased from 5.79 ± 0.31 mEq/L at baseline to 5.39 mEq/L during treatment, a mean decrease = 0.4 mEq/L (p=0.08). The mean fecal potassium excretion increased from 616 ± 203 mg/day during baseline to 975 ± 399 mg/day during treatment (P=0.02). The proportion of days with serum potassium < 5.5 mEq/L was 38% during the baseline period and 67% during the treatment period..

This current protocol includes an initial dose of patiromer of 8.4g once daily to be administered with the morning or mid-day meal. This will be titrated according to the pre-dialysis potassium values in weeks 1, 2 and 3 of the protocol.

3.5 Adverse events with patiromer

In the published clinical trial of patiromer that was the longest duration (52 weeks), hypomagnesemia (7.2%) was the most common treatment-related adverse event, mild to moderate constipation (6.3%) was the most common gastrointestinal adverse event, and hypokalemia (<3.5 mEq/L) occurred in 5.6% of patients ²⁸.

3.6 Potential for drug-drug interactions with patiromer

Patiromer has the potential to bind many orally administered medications. However, few formal drug interaction studies have been conducted in humans. The package insert notes that twenty-eight drugs were tested to determine the potential for interaction with patiromer. Fourteen of the drugs tested did not show an *in vitro* interaction with patiromer (acetylsalicylic acid, allopurinol, amoxicillin, apixaban, atorvastatin, cephalexin, digoxin, glipizide, lisinopril, phenytoin, riboflavin, rivaroxaban, spironolactone and valsartan). Twelve of the 14 drugs that showed an *in vitro* interaction were subsequently tested *in vivo*. The package insert cites studies in healthy volunteers which showed that patiromer did not alter the systemic exposure of amlodipine, cinacalcet, clopidogrel, furosemide, lithium, metoprolol, trimethoprim, verapamil or warfarin when coadministered. Patiromer decreased the systemic exposure of co-administered ciprofloxacin, levothyroxine and metformin.

However, there was no interaction when patiromer and these drugs were taken three hours apart. To account for this, patiromer should be administered at least 3 hours before or 3 hours after other oral medications.

4. Study objectives

4.1 Primary endpoint

To determine if patiromer administered orally once a day with the morning or mid-day meal will reduce frequency of episodes of hyperkalemia in ESRD patients who receive thrice-weekly HD.

4.2 Secondary endpoints

1. To determine whether patiromer can effectively be used in place of one dose of phosphate binder per day
2. To determine the between-group differences in percent of patients with serum $K > 5.5$ mEq/L
3. To determine the efficacy and dosing of patiromer in ESRD patients.
4. To determine the between-group differences in need for additional hemodialysis treatments due to hyperkalemia
5. To determine the between-group differences in pre-specified significant arrhythmia events as detected with cardiac monitors in Week 4.
6. To determine the between-group differences in serum albumin and PTH concentrations.
7. To determine feasibility of a large-scale hemodialysis-based trial.
8. To determine the change in serum potassium concentration two weeks after study drug is discontinued
9. To determine the change in serum phosphorus concentration two weeks after study drug has been discontinued
10. To develop procedures and instruments to be employed in a large scale clinical trial.

5. Selection and withdrawal of subjects

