6.6 Randomization

Randomization will occur at any time in Week 0 prior to HD3. This will be done using the REDCap system and will assign patients 1:1 to either continue usual care or to receive patiromer as detailed below.

6.7 Open-label patiromer and dose titration, Weeks 1, Week 2, Week 3, Week 4.

Patients randomized to the patiromer arm will initiate on 8.4 g/day (one pack) given once a day with breakfast or lunch, to start after HD3 at the end of Week 0. The patient is instructed to not take any other medications for three hours before or three hours after patiromer.

The patiromer dose will be titrated based on serum potassium concentrations on HD1 of weeks 1, 2, and 3. Patiromer will be increased by 8.4 g/day if $K \geq 5.5$ meq/L, decreased by 8.4 g/day if $K < 4.5$ mEq/L, and patiromer will be discontinued if $K < 4$ mEq/L.

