If a subject does withdraw from the study, the Investigator must make every effort to perform all post-study assessments. Safety and tolerability data on the subject will be evaluated and reported. The Investigator may withdraw a subject due to non-compliance with the protocol requirements, or if an event occurs which would interfere with the objectives of the study.

Subjects must be withdrawn from the study if:

1. Informed consent is withdrawn voluntarily by the subject.
2. The Investigator believes it is in the best interest of the subject to be removed from the study.
3. The serum potassium levels exceeds 7 mEq/L during Week 2 to 7 and, the first sample is confirmed by a second sample exceeding 7 mEq/L at an unscheduled visit within one week.

4. A serious adverse event occurs (the Investigator must consider severity of the event and relatedness to study medication).

5. A significant protocol violation occurs.

The date and reason for discontinuation must be noted and a brief discontinuation summary must be filled out. Serious Adverse Events should be followed up until resolution or for 30 days after discontinuation. All efforts should be made to have subjects that discontinue from study return the remainder of their study medication.

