Randomization ¹			X													
Initiation of Patiromer ²				X												
Patiromer titration ³					X			X				X		X		
Physical Exam		X														
Vital Signs ⁴ (BP, HR, Height, Weight)		X			X				X			X		X		X
Renal Function Panel		X														
Serum Potassium			X	X	X				X			X	X	X	X	X
Serum Magnesium		X							X			X				X
Serum Pregnancy Test ⁵		X														
Holter Monitor Applied	X															X
Holter Monitor Removed			X													
Previous medication and concomitant medication		X	X	X	X				X			X		X	X	X
Adverse Event Questioning		X	X	X	X				X			X		X	X	X
Dialysis ⁶																
ECG	X	←								→						

1=Randomization can occur at any point after Week 0 HD1 as long as it is completed prior to Week 0, HD3.

2=If randomized to the Patiromer Arm

3=Patiromer will be increased by 8.4 g/day if K \geq 5.1 mEq/L, decreased by 8.4 g/day if K<4.0 mEq/L, and discontinued if K<3.5mEq/L

4= Blood Pressure taken after sitting for 5 minutes; Height only collected at Week 0, HD1

5=Females of child bearing potential

6= Hemodialysis should be performed 3 times per week

BIBLIOGRAPHY

6. System USRD. 2017 USRDS annual data report: Epidemiology of kidney disease in the United States. Bethesda, MD: National Institutes of Health, National Institute of Diabetes and Digestive and Kidney Diseases; 2017.

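### The dosing objective supports only a description of dose under titration, and without packet counts for every treated patient that description covers prescribed dose, not dose taken

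*Combined protocol and SAP*

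**What the plan says.** Secondary objective 3, in the synopsis and in section 4.2, reads "To determine the efficacy and dosing of patiromer in ESRD patients". Section 8.2 attaches no dosing endpoint or analysis to it. Laboratory values are to be compared between the randomised groups by ANOVA, and secondary measurements are called exploratory.

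Section 6.6 states that randomisation "will assign patients 1:1 to either continue usual care or to receive patiromer". Under section 6.7 every patiromer patient "will initiate on 8.4 g/day (one pack) given once a day with breakfast or lunch", and then "The patiromer dose will be titrated based on serum potassium concentrations on HD1 of weeks 1, 2, and 3". The rule there is "Patiromer will be increased by 8.4 g/day if $K \geq 5.5$ meq/L", a decrease of the same size below 4.5 mEq/L, and "patiromer will be discontinued if $K < 4$ mEq/L". Sections 6.13 and 6.14 repeat it. Footnote 3 of the section 10 schedule gives a different rule: an increase from 5.1 mEq/L, and "decreased by 8.4 g/day if K<4.0 mEq/L, and discontinued if K<3.5mEq/L".

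On returned drug, section 6.15 says: "All efforts should be made to have subjects that discontinue from study return the remainder of their study medication". Section 7.1 sends remaining patiromer back to the sponsor at study end and mentions no count by patient. Section 6.12 leaves study medication out of the medication record. Neither the visits in 6.13 and 6.14, nor dispensing in 7.2, nor the schedule as it can be read lists a packet count, diary or adherence check.

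**The concern.** Two things limit what the trial can say about dosing.

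First, dose is a consequence of potassium. A patient whose potassium is high on an HD1 sample is moved up, and one whose potassium is low is moved down or stopped. The dose reached therefore carries information about the patient's underlying potassium and response. A table of potassium control by dose would mix that with any effect of dose.

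Second, intake is not measured in patients who complete. Someone who leaves the packets unopened tends to keep a high potassium, is prescribed more, and enters the dose summary at the higher figure.

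Objectives 7 and 10 and section 8.1 say the study is meant to prepare a large trial. A dose summary is a natural input to that trial, although the protocol does not say it will be used so. Intake cannot be reconstructed once the packets are gone.

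**Working it through.** **1. The plan's own figure.** Section 8.1 gives 86% power for n = 20 per group, difference 2, SD 2, alpha 0.05 (sidedness not stated). Noncentrality = 2 / (2 × √(2/20)) = 3.16 on 38 df. A two-sided t-test gives 86.9%, so the figure reproduces (a normal approximation gives 88.5%). It concerns the randomised comparison and does not depend on this point.

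**2. Inputs for a model of the titration rule.**
- From section 3.4 (six hemodialysis patients): mean potassium 5.79 ± 0.31 mEq/L, with 0.31 taken as the between-patient SD.
- From section 3.4: a fall of 0.4 mEq/L on 4.2 g three times daily, which is 12.6 g/day. If linear (assumed), the fall per 8.4 g packet is 0.4 × 8.4/12.6 = 0.267 mEq/L.
- Assumed: within-patient SD 0.5 and full effect by the next visit.
- Section 6.7 thresholds at three HD1 values, then six later samples scored at ≥ 5.5.

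**3. Correlation of final dose with Week 3–4 episodes.** The first column uses a wholly assumed population (mean 5.4, between-patient SD 0.45). The second uses the section 3.4 values. Intake is complete.

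| True fall per packet (mEq/L) | Mean 5.4, SD 0.45 | Mean 5.79, SD 0.31 |
|---|---|---|
| 0 | +0.65 | not run |
| 0.1 | +0.47 | not run |
| 0.2 | +0.24 | −0.01 |
| 0.267 | +0.09 | −0.18 |
| 0.4 | −0.15 | not shown |

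With the section 3.4 inputs, 0.267 per packet and 20% taking nothing, −0.18 becomes +0.15. The sign is not fixed by the design.

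**4. Trials of 20 treated patients** (1,000 per scenario; true slope −0.267 mEq/L per packet; mean 5.5 or 5.79; between-patient SD 0.2–0.7; within-patient SD 0.3–0.5; both threshold sets).
- The mean across-patient slope of potassium on final dose ran from −0.16 to +0.24. It was always biased upward and sometimes reversed.
- The slope of episodes on dose was positive in 89–100% of trials at between-patient SD 0.5 or more, and in 20–46% at SD 0.2.
- With a stronger assumed effect of −0.5 per packet, the mean potassium slope was −0.35 to −0.01: attenuated, not reversed.
- The within-patient change after a Week 1 increase was −0.32 to −0.80 against a true −0.267. By regression to the mean, that analysis errs in the drug's favour.

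**5. Prescribed against taken dose** (section 3.4 inputs, 0.267 per packet, section 6.7 thresholds). Takers are prescribed a mean of 17.7 g/day and non-takers 25.4 g/day. For an assumed share p taking nothing, prescribed = (1 − p) × 17.7 + p × 25.4, and taken = (1 − p) × 17.7.

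| p | Prescribed (g/day) | Taken (g/day) | Gap |
|---|---|---|---|
| 10% | 18.5 | 15.9 | 2.5 |
| 20% | 19.2 | 14.2 | 5.1 |
| 30% | 20.0 | 12.4 | 7.6 |

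Repeat runs at 20% give 19.2 to 19.3 prescribed and 14.1 to 14.2 taken. Of the 5.1 g gap, 0.2 × 17.7 = 3.5 g is dose that non-takers would have been credited with anyway, and 0.2 × (25.4 − 17.7) = 1.5 g comes from escalating them. With mean 5.4 and SD 0.45, the 20% figures are 12.5 prescribed against 9.0 taken.

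**6. The threshold conflict.** With the section 3.4 inputs and complete intake, the mean dose is about 17.7 g/day under the section 6.7 thresholds and about 24.4 under footnote 3. That difference exceeds the 20% non-taker gap.

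**The case against.** The strongest reply is that the plan contains no dose–outcome analysis. The efficacy half of objective 3 is served by the randomised comparison. The dosing half can be read simply as which doses patients reach under titration, and secondary results are already labelled exploratory in a proof-of-concept study. All of this stands. On its own, the wording of the objective would not justify a change.

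A reader might infer that any dose–outcome result is reversed by design. The documents do not support that. At the effect implied by section 3.4, the modelled correlation with complete intake is close to zero or negative, and clear reversal needs a weaker effect, a wider spread between patients, or non-intake. What can be said is that the comparison is confounded by response.

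A reader might also infer that no drug is recovered except from those who discontinue. Section 7.1 does return remaining patiromer at study end. It states no collection or count by patient, so it does not measure intake.

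Exclusion criterion 1 removes patients judged non-adherent before entry. This should lower the share of non-takers, and 20% may be too high. It rests on a physician's opinion at entry and does not measure intake during the trial.

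**Conclusion.** The point holds in limited form. Dose levels are not randomised, so comparing outcomes across doses would give a biased answer whose sign cannot be predicted from the design. No such comparison is planned, and the primary endpoint, its power and the randomised efficacy comparison are untouched. The firmer finding is that intake goes unmeasured in completers, so the reported dose would be prescribed dose.

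The size of that gap rests on an unknown rate of non-intake. The range of 2.5 to 7.6 g/day in the working also assumes a linear effect taken from six patients, an assumed within-patient SD, all-or-nothing intake and the section 6.7 thresholds. This is a cheap improvement worth making before enrolment, not a flaw that undermines the trial.

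**What to change.** - In sections 6.13, 6.14 and 7.2, and as a row in the section 10 schedule, record packets dispensed to each patiromer participant. Have every participant bring unused packets to the existing HD1 visits and at the end of dosing, and count them.
- Report mean packets taken per day, (dispensed − returned) / days, beside the prescribed dose. Discarded packets would count as taken, so this is an upper bound on intake.
- Word objective 3 as describing the distribution of prescribed and taken dose under the titration rule, and state in 8.2 that no causal comparison between dose groups will be made.
- Reconcile the titration thresholds in 6.7, 6.13 and 6.14 with footnote 3 of section 10 before any dose is described.

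The cost is a few minutes of counting per visit and some text edits. No dose, visit or blood sample is added by the counting.
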